After enrollment and prior to the first assessment, participants will be assigned to the intervention or the control group through randomization by minimization. MinimPy will be used to randomize the participants based on age (2 levels: <8 years and >8 years) and GMFCS score (3 levels: I, II and III) (Saghaei, 2011). The allocation ratio will be 1:1 with probability set at 0.75. The biased coin minimization will be used as probability method and marginal balance as distance measure.

Assessments are planned in the University Hospitals and special needs schools, at baseline (PRE) and after the 12-week control or intervention period (POST). Training and assessments will always be

conducted on different days. Participants in the intervention group start training within 2 weeks after the baseline assessment. For both groups, the POST assessments will be performed within 1 week after the 12-week period. Blinding is not completely possible since participants and trainers are aware of group allocation. Assessors are also aware of group allocation during assessments but data will be anonymized before processing and analyses. The participants will be assessed by the same assessors (PRE and POST) and the data of one participant will be processed by the same processor.

Piloting for the feasibility of the measurements and parameter extraction was done through prior and parallel investigations. The exercises used during the training were piloted through iterations with strength and conditioning specialists to ensure correct exercise selection and also with senior pediatric physiotherapists and their patients to ensure the applicability in targeted population of children with SCP.

Sample size

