At the moment of trial design (2018), no data were available on an RCT investigating changes in muscle size after PRT in a population of children with SCP. Therefore, effect sizes (d) of systematic reviews and meta-analyses reporting muscle strength outcomes after PRT were used. Reported effect sizes were moderate ($d=0.53$) (Ryan et al., 2017) and large ($d=1.050$ and $d=1.105$) (Park & Kim, 2014). Based on a large effect size of $d=0.8$ with the probability of making a type I error set equal to or less than 1% ($p\leq 0.01$) and a power of 80%, an independent samples t-test with common standard deviation required 39 independent observations per group to compare the evolution over time between the intervention and control groups. To account for the possibility of clustered legs in bilaterally affected participants a design effect (Killip et al., 2004) was calculated resulting in an estimated sample size of clustered observations per group with following formulas:

$$\text{Design effect} = 1 + \rho * (m-1),$$

where ρ is the intraclass correlation and m the cluster size, and,

$$\text{Estimated sample size of clustered legs} = \text{estimated sample size of independent observations} * \text{design effect} = m * \text{number of participants}$$

With a cluster size of $m=2$ (2 legs per bilaterally affected participant) and an intraclass correlation coefficient of $\rho=0.1$, based on literature of general health parameters (Adams et al., 2004), the estimated design effect was 1.1, resulting in 43 clustered legs, or 22 bilaterally affected participants per group. A group including both uni- and bilaterally affected children would require a sample size between 39 and 43.

Intervention

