To define the effects of the PRT intervention linear mixed models will be applied to evaluate the difference in evolution over time between the control and intervention group (time*group interaction effect) and between PRE and POST within each group (time effect). The random effects in these models can correct for the correlation between repeated observations within the same subject. Moreover, in the case of missing values that are completely at random, i.e. not related to any observed or unobserved outcomes, or at random, i.e. related to observed outcomes, linear mixed models provide valid inferences for missing observations. A covariance structure for repeated measurements to model longitudinal dependencies within the participant will be applied with a random intercept for participant (legs are nested within participants). The models will be adjusted for age and GMFCS level as covariates as these were used to allocate the children to the control or intervention group. Age was entered as a categorical variable (<8 years and >8 years). A full-factorial time*group mean model adjusted for age and GMFCS level, with a compound symmetry covariance matrix, unless an unstructured covariance matrix results in a better fit (Akaike information criterion decrease of >2). Adjustment for age (categorical variable: <8 years and >8 years) and GMFCS level will be included as these were used to allocate the children to the control or intervention group.

The α -level will be adjusted to $p \leq 0.01$ since multiple parameters are evaluated for most research questions, with a maximum of 5 parameters (functional strength). All analyses will be performed with SPSS (Version 28, SPSS Inc., Chicago, Illinois).

Finally, the data of the total intervention group (intervention + waitlist control group with delayed intervention) will be used to define the association between baseline properties and the changes in the outcome parameters after PRT with uni- or multivariate regression (mixed) models.

References

<https://doi.org/10.1016/j.jclinepi.2003.12.013>

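### The training effect is tested as an unadjusted difference in PRE-POST change; adjusting for the PRE value would usually be more precise at no extra data cost

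*Combined protocol and SAP*

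**What the plan says.** Section 6 (Statistics) of the combined protocol and SAP applies linear mixed models to "evaluate the difference in evolution over time between the control and intervention group (time*group interaction effect"). The mean structure is "A full-factorial time*group mean model adjusted for age and GMFCS level, with a compound symmetry covariance matrix", with an unstructured covariance matrix instead if it lowers the AIC by more than 2. A random participant intercept handles legs nested within children. Only two covariates are named: "The models will be adjusted for age and GMFCS level as covariates as these were used to allocate the children to the control or intervention" arm. Nowhere is the outcome's PRE value a covariate in this test, and nowhere are the PRE means of the two arms set equal. Baseline properties serve as predictors only in the later association analysis of all trained children.

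The Sample size section uses the same contrast: 39 independent observations per group "to compare the evolution over time between the intervention and control groups".

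Two statements under Study design limit the choice of remedy. On timing: "After enrollment and prior to the first assessment, participants will be assigned to the intervention or the control group through randomization by minimization". On blinding: "Assessors are also aware of group allocation during assessments". The same section says that the same assessors see a child at both visits.

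**The concern.** A full-factorial time-by-group model estimates a separate PRE mean in each arm. Minimization balances two age levels and GMFCS level, but not the PRE value of each outcome. A chance PRE difference between arms therefore enters the estimated effect with full weight. A regression on PRE would give it only the weight that the PRE-POST relation supports.

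At stake is precision: wider intervals and lower power than the data could give, in a small trial tested at alpha 0.01. The effect size used (0.8) also lies above the smallest one the Sample size section cites (0.53), so there is little power to spare.

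**Working it through.** **Inputs.** From the Sample size section: d=0.8, alpha 0.01, power 80%, design effect 1.1. From Study design: 1:1 allocation and assessments at PRE and POST. Assumed, because the documents do not give them: r, the PRE-POST correlation given age and GMFCS level (range 0.5 to 0.9); similar PRE and POST SDs; d expressed in SDs of change; a two-sided test (sidedness is not stated, but one-sided versions give 32 to 33 per group, not 39).

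**1. The plan's figure.** A two-sample t-test by the noncentral t distribution has power 79.8% at 38 per group and 81.0% at 39, so 39 is reproduced. Then 39 × 1.1 = 42.9, giving 43 legs, and 43/2 gives 22 bilaterally affected children per group. All three figures agree with the plan.

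**2. What the interaction estimates.** With two visits and complete pairs, the time-by-group term is (POST mean − PRE mean) in the intervention arm minus the same in the control arm. Fitting the planned model to simulated data gave this difference to within rounding error (about 1e-14) under both compound symmetry and unstructured covariance. Age and GMFCS main effects are the same at both visits, so they cancel. Neither they nor the choice of covariance matrix recovers the precision.

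**3. Variance ratio.** With equal SDs σ:
- change score: 2σ²(1−r)
- POST adjusted for PRE: σ²(1−r²)
- ratio, adjusted to change: (1−r²) / [2(1−r)] = (1+r)/2

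**4. Power.** The effective d is 0.8/√((1+r)/2), put back into the calculation of step 1.

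| r (assumed) | Variance ratio | Power at 39 per group | n per group for 80% power |
|---|---|---|---|
| planned test | 1 | 81.0% | 39 |
| 0.5 | 0.75 | 92.1% | 30 |
| 0.7 | 0.85 | 87.9% | 33 |
| 0.8 | 0.90 | 85.7% | 35 |
| 0.9 | 0.95 | 83.3% | 37 |

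If the true effect were the cited 0.53, read on the same scale, power at 39 per group would be 38.7% as planned, against 52.7% (r=0.5), 46.3% (r=0.7) or 41.0% (r=0.9).

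**5. Finite-sample check.** Simulation with biased-coin minimization and estimated covariate effects gave ratios of 0.76, 0.87, 0.92 and 0.98 at 39 per group for r = 0.5, 0.7, 0.8 and 0.9. At 22 per group they were 0.76, 0.89, 0.94 and 0.98, with Monte Carlo error of a few hundredths. The formula is therefore slightly generous at high r.

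**6. Unequal SDs.** With k = POST SD / PRE SD, the large-sample ratio is k²(1−r²) / (1 + k² − 2rk).
- r=0.7, k=1.1: 0.6171/0.67 = 0.92, not 0.85
- r=0.8, k=1.25: 0.5625/0.5625 = 1.00
- r=0.9, k=1.1: 0.2299/0.23 = 1.00

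In the last two cases nothing is gained.

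**7. Distorted measurement.** Take a group-related shift of 0.10 SD with equal SDs. If it occurs at PRE only, it moves the change-score estimate by 0.10 SD and the adjusted estimate by r times that: 0.07 at r=0.7 and 0.09 at r=0.9. If it occurs at both visits, it cancels in the change score but leaves (1−r) times the shift in the adjusted estimate: 0.05, 0.03 and 0.01 at r = 0.5, 0.7 and 0.9.

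**The case against.** The strongest reply is that nothing here is an error. The planned test is unbiased under randomization, its simulated type I error at nominal 1% was 0.8%, and the sample size was computed for exactly this contrast. That stands: the point concerns efficiency only.

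The size of the gain is also open to challenge. No r is given, and strength and functional scores are averages of three trials, which pushes r up and the gain down by an unknown amount. The (1+r)/2 ratio also needs similar SDs. These limits stand, so it cannot be said that every outcome would benefit.

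A reader might infer that PRE adjustment also protects against distorted PRE measurements, since PRE follows allocation and assessors know the group. The documents do not support that. Because the same assessors see each child at both visits, a shift that persists from PRE to POST is plausible, and the change score then does better (step 7). Which estimate is safer depends on the kind of distortion, and neither removes it in general.

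A reader might also infer that adjustment costs nothing. Constraining the PRE means to be equal would keep children with one visit, but it relies on a PRE unaffected by allocation, which is less secure here. Regressing POST on PRE avoids that constraint, but it drops children with one visit, gives no within-group time effect, and would ignore clustering if the participant intercept were left out. These costs are real but manageable.

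**Conclusion.** The concern holds as a matter of precision. The plan's between-group test is valid and correctly sized, but it is usually less precise than the data allow. Under similar PRE and POST SDs, d=0.8 on the change scale and two-sided alpha 0.01, PRE adjustment raises power at 39 per group by about 11 percentage points at r=0.5 (92.1 − 81.0), 7 at r=0.7 (87.9 − 81.0), 5 at r=0.8 (85.7 − 81.0) and 2 at r=0.9 (83.3 − 81.0). It is worth having at moderate r, is small at r of 0.9 or more, and can disappear when the POST SD is clearly larger than the PRE SD. The text does not support reading this as bias, an inflated type I error or a wrong sample size.

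**What to change.** In section 6 (Statistics), make the between-group test a model of POST on group, the outcome's PRE value, age category and GMFCS level. For leg-level outcomes use that leg's own PRE value, and keep the random participant intercept wherever both legs are analysed. Keep the planned time-by-group mixed model for two purposes: the within-group PRE-POST effects, and a sensitivity analysis that retains children with only one visit. State how children missing PRE or POST are handled in each model. Do not make the equal-PRE-means version the main analysis, given the timing of PRE and the unblinded assessors, and do not present the adjustment as general protection against PRE distortion.

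The cost is SAP wording and one extra SPSS model per outcome, with no new data. The downside to name in the plan is that children with a single visit drop out of the adjusted model.

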A previously validated 3-dimensional freehand ultrasonography technique will be used to evaluate muscle morphology, combining a 2-dimensional B-mode ultrasonography device (Telemed-Echoblastar 128 Ext-1Z, with a 5.9 cm 10MHz linear ultrasound transducer, Telemed, Ltd, Lithuania) with a motion tracking system (Optitrack V120:Trio, NaturalPoint, Inc, Corvallis, Oregon, USA) (Cenni et al., 2016). Ultrasound settings will be kept constant throughout the study period, at a frequency of 8MHz, with a focus of 3cm, a gain of 64%, a dynamic range of 56 dB and unaltered time-gain compensation. Depth can vary between 5cm and 7cm, adjusted to muscle size. The m. rectus femoris and m. tibialis anterior will be scanned in supine position with a triangular cushion underneath the calf, providing approximately 25 degrees of knee and hip flexion. The m. semitendinosus and m. medial gastrocnemius will be scanned in prone position with a triangular cushion underneath the shank, providing 25 degrees of knee flexion and an unconstrained ankle angle. STRADWIN software (version 6.0; Mechanical Engineering, Cambridge University, Cambridge, UK) will be used for data acquisition, generation of 3-D datasets, and data processing. Data processing will be performed by experienced processors, drawing equally spaced transverse plane segmentations throughout the 3-D datasets, which will be interpolated with an automatic cubic planimetry technique resulting in the muscle volume (in mL) (Treece et al., 1999). Muscle length (in mm) will be defined by calculating the linear distance between muscle origin and muscle tendon junction. Both muscle volume and muscle length will be normalized to fibula length to correct for skeletal growth (mL/cm and cm/cm). The echo-intensity (EI) from ultrasound images will be used as an indication of intrinsic muscle quality, with higher EI-values representing an increased ratio of non-contractile vs. contractile tissue (Pitcher et al., 2015; Young et al., 2015). EI (expressed in arbitrary units) will be computed as the average value throughout the interpolated reconstruction of the muscle.

4. Functional strength assessments

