Endurance functional strength will be assessed with 30-s repetition maximum tests including bi- and unilateral heel raise, sit-to-stand, and lateral step-up, as previously described (van Tittelboom et al., 2021). Participants completed as many repetitions as possible in 30 seconds. Each test will be 3 times and the average taken as final score. Explosive strength will be evaluated with a standing long jump, with both feet together, which will also be repeated 3 times and the scores averaged. The use of orthoses will not be allowed, as the PRT program will also be performed without orthoses.

5. Gross motor function and walking capacity

Gross motor function will be evaluated with the Gross Motor Function Measure-Item Set (Brunton & Bartlett, 2011) and the Gross Motor Ability Estimator 2 used to estimate the final score. The 1-minute walk test, performed on an indoor 20-m track, will be used to assess walking capacity (Chrysagis et al., 2014; McDowell et al., 2009). The participant will be instructed to walk as fast as possible without running and the distance covered in 1 minute will be recorded. Both assessments will be performed without orthoses, but a key-walker is allowed for the 1-minute walk test for children classified as GMFCS-level III.

6. Statistics

Descriptive statistics for all groups will be summarized using appropriate summary indices. The comparison between TD children and children with CP will be performed with a Student's *t*-test (after confirming equality of variances) or the Mann-Whitney *U*-test. Associations between muscle morphology measures, muscle strength and participant characteristics will be evaluated with univariate linear regressions followed by a multivariate linear regression using a backward approach. The linear regressions in the TD cohort based on an anthropometric variable will be used to define the deficits in muscle strength and muscle morphology in CP children.

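### The basis given for the fixed 0.01 (at most five parameters) fits functional strength but cannot be verified for muscle morphology; name the tested families, and use Holm in place of fixed 0.01 at no cost in sample size

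*Combined protocol and SAP*

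**What the plan says.** Section 6 (Statistics) sets one significance level, 0.01, for all analyses. The reason given is a count per research question: "since multiple parameters are evaluated for most research questions, with a maximum of 5 parameters (functional strength"). It does not list the research questions, the parameters in each, the family-wise level aimed at, or the name of a multiplicity procedure.

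The five can be found in section 4 (Functional strength assessments): "30-s repetition maximum tests including bi- and unilateral heel raise, sit-to-stand, and lateral step-up" make four, and "Explosive strength will be evaluated with a standing long jump" is the fifth.

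Section 3 (Three-dimensional freehand ultrasonography) describes four muscles: "The m. rectus femoris and m. tibialis anterior will be scanned in supine position" and "The m. semitendinosus and m. medial gastrocnemius will be scanned in prone position". It describes three properties. Two are size measures ("Both muscle volume and muscle length will be normalized to fibula length to correct for skeletal growth"). The third is echo-intensity, presented as an indicator of muscle quality.

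Where section 6 names morphology, it does so as a whole and for the baseline questions: "Associations between muscle morphology measures, muscle strength and participant characteristics will be evaluated with univariate linear regressions", and the regressions in typically developing children are "used to define the deficits in muscle strength and muscle morphology in CP children". For the training effect it specifies a mixed model with a time-by-group interaction and a PRE to POST comparison within each group. It does not say which morphology parameters enter that model.

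**The concern.** The 0.01 rests on a count that the reader can confirm for one outcome domain and not for another. Counted by assessment section, as functional strength evidently was, morphology has more than five parameters. Whether 0.01 then delivers the implied 5% depends on a grouping that is not written down. Muscle morphology is not peripheral here: hypertrophy is a stated training target (Intervention), and the Sample size section says no randomised data on muscle size after such training existed at design. A reader of those results could not tell whether the error rate is about 4% or up to about 11%.

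There is a second, smaller matter. Even where the count is right, testing all five outcomes at a fixed 0.01 gives up power that a step-down procedure recovers at the same family-wise level.

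**Working it through.** **1. The plan's own figures.** 0.05 / 5 = 0.01, which matches. The Sample size section uses d = 0.8, type I error 1% and power 80%. A two-sided two-sample t-test (noncentral t) needs 39 per group, with power 81.0% at 39, which matches the stated 39. With the design effect, 39 × 1.1 = 42.9, so 43 legs, or 22 bilaterally affected children, per group.

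**2. Parameters by assessment section.**

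| Domain | Count |
|---|---|
| Isometric strength (three muscle groups) | 3 |
| Functional strength (four 30-second tests and long jump) | 5 |
| Gross motor function and walking | 2 |
| Morphology, 4 muscles × 3 properties | 12 |
| Morphology without tibialis anterior (in no trained group), 3 × 3 | 9 |

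**3. Family-wise error at fixed 0.01.** Under independence it is 1 − 0.99^k. With a common correlation ρ it is 1 − ∫ φ(z)[Φ((c − √ρ z)/√(1−ρ)) − Φ((−c − √ρ z)/√(1−ρ))]^k dz, where c is the two-sided 1% normal critical value. All correlations are assumptions.

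| k | independent | ρ = 0.3 | ρ = 0.5 | ρ = 0.7 |
|---|---|---|---|---|
| 12 | 11.4% | 10.1% | 8.3% | 6.0% |
| 9 | 8.6% | 7.9% | 6.7% | 5.1% |

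The error comes down to 5% at a common correlation of about 0.78 (12) or 0.71 (9). For comparison, independent families of 5, 4 and 3 give 4.9%, 3.9% and 3.0%. A split by property (4 or 3 each) or by muscle (3 each) therefore keeps morphology within 5%.

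**4. Holm in the functional-strength family.** The thresholds are 0.05/(5 − i + 1): 0.0100, 0.0125, 0.0167, 0.0250, 0.0500. None is below 0.01, so every result significant at 0.01 stays significant.

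**5. Power.** Simulated t-tests, 20,000 runs per scenario, d = 0.8 for responding outcomes, assumed correlation 0.5, average power per responding outcome:

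| Responding | n per group | Holm | fixed 0.01 |
|---|---|---|---|
| 5 of 5 | 39 | 0.89 | 0.81 |
| 3 of 5 | 39 | 0.84 | 0.81 |
| 1 of 5 | 39 | 0.81 | 0.81 |
| 5 of 5 | 22 | 0.59 | 0.49 |

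No run lost a rejection made at 0.01.

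**6. Downside within the family.** When four of five outcomes respond (39 per group), false positives on the fifth rise from about 1% to about 3% to 4%, still within 5%.

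**7. Error across families.** Take six independent families of 3, 5, 2, 4, 4 and 4, which is 22 tests. Fixed 0.01 gives 1 − 0.99^22 = 19.8%. Holm at 0.05 in every family gives at most 1 − 0.95^6 = 26.5%. Holm with 0.01 as its first step (family level 0.01 × family size) gives at most 1 − 0.97 × 0.95 × 0.98 × 0.96^3 = 20.1%.

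**The case against.** The plan counts per research question and says that the largest count is five. Taken at its word, no morphology question has 9 or 12 parameters, and the higher error rates arise only when assessment sections are put in place of research questions. **This stands in part.** A reader might infer that morphology is one family and that its error rate is 11.4%. The documents do not support that: section 3 describes what is measured and not what is tested, and it sets echo-intensity apart as muscle quality, so a split is plausible. Nor is a split the only way to satisfy the sentence, since testing five or fewer morphology parameters would also do it. What remains is that neither is written.

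A reader might also suspect that the level could be chosen after seeing results. It could not: 0.01 is fixed in advance and agrees with the sample size. The uncertainty is in the error rate implied for it.

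Fixed 0.01 is valid for five tests, and Holm is not needed to cure the missing list. **Both are true.** Holm is offered as an improvement, not as the correction of an error. Holm at 0.05 in every family would also raise error across families (up to 26.5% against 19.8%), so it is not recommended for the smaller ones.

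The power at 39 per group is a favourable case. **This stands.** Bilateral heel raise, sit-to-stand and the two-footed long jump give one value per child, and the Sample size section allows 22 bilaterally affected children per group. The 0.89 should not be read as the trial's power for functional strength; at 22 it is about 0.59 against 0.49.

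Finally, five parameters are not five tests. With the interaction and a PRE to POST test in each of two groups, functional strength has 5 × 3 = 15. Every error rate above counts only the interaction, so the family definition has to say so.

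**Conclusion.** The concern holds as a gap in the basis for 0.01, together with a cheap gain in power. The stated maximum is correct for functional strength. For morphology it is correct only under a split, or a selection of five or fewer parameters, that the plan does not state. With a split by property or muscle, 0.01 keeps each morphology family at or below 3.9%; as a single family it would allow 6.7% to 11.4% for correlations between 0.5 and 0. It is not shown that the plan exceeds 5%, only that a reader cannot check.

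For the five functional-strength interactions, Holm at 0.05 is never worse than fixed 0.01 in rejections and holds the same 5%. It adds about 8 points of average power at 39 per group, or 10 at 22, if all five respond, and nothing if one does.

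Assumptions: the 0.05 family level is inferred from 0.05/5; correlations are assumed; power is for simple t-tests at d = 0.8, not for the planned mixed model. The change should be made, but the trial does not depend on it.

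**What to change.** Amend the multiplicity sentence in section 6 to do four things.

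- **Name the families** for the time-by-group interaction: isometric strength (3); functional strength (5); gross motor function and walking (2); and muscle volume, muscle length and echo-intensity as three separate families of 4, or of 3 if limited to the trained muscle groups. Say which muscles are tested. The maximum of five is then true as written.
- **Functional strength:** replace fixed 0.01 with Holm at family level 0.05.
- **Families of 2 to 4:** use Holm with 0.01 as the first step, so the family level is 0.02, 0.03 or 0.04. Error across families then hardly changes (at most 20.1% against 19.8% over 22 independent tests). State that control is within families only.
- **Within-group PRE to POST tests:** state that they lie outside the families and are supportive only.

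The cost is a few lines of SAP text and ordering the p-values within each family. No rejection at 0.01 is lost and the sample size stands. The price is the higher false-positive rate on a non-responding functional outcome when the others respond (about 3% to 4% instead of 1%).

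Keeping morphology as one family at 5% would cost more. An isolated effect would have to reach 0.05/12 = 0.0042 or 0.05/9 = 0.0056, with power 0.72 or 0.75 instead of 0.81 at 39 per group and d = 0.8.
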